Study design	
This is an international, non-interventional research study of adult patients with FD and their caregivers. The study will comprise a prospective time and motion evaluation and a cross-sectional evaluation of patient and caregiver-reported outcomes. Patients' demographic characteristics will be collected from hospital medical records.
 
For the cross-sectional evaluation of patient and caregiver-reported outcomes, patients with FD and their caregivers will be asked to complete a series of questionnaires, to include validated measures of HRQoL, wellbeing and work productivity (for patients) and work productivity and the strain of care provision (for caregivers). Patients and caregivers will also complete a bespoke questionnaire to evaluate the total time associated with attending the hospital or treatment centre for a single ERT administration visit, and time away from work. In addition, patients will also be asked about their level of fatigue using a bespoke Likert scale. With the exception of the work productivity questionnaire and Fatigue Likert scale, the study questionnaires will be completed at a single point in time, when the patient attends the hospital or treatment centre for administration of ERT. The work productivity questionnaire (which has a recall period of seven days, excluding the day of completion) will be completed twice; the first work productivity questionnaire will be completed 1-7 days after receiving a dose of ERT (ideally within 2 days), to capture a seven day period that includes an ERT administration visit and the second questionnaire will be completed on the day the patient attends the hospital or treatment centre to receive their next dose of ERT (to capture a seven day period that does not include ERT administration). The Fatigue Likert scale will be completed three times; during an ERT administration visit, on the evening of the visit and the next day.

	Separate patient consent will be obtained for the time and motion evaluation and for the cross-sectional evaluation of patient-reported HRQoL, wellbeing, levels of fatigue and work productivity; thus, patients who do not wish to complete the study questionnaires will remain eligible for the time and motion study (and vice versa), provided that consent has been obtained.

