- The strain of providing care for a patient with FD will be assessed using the CSI. The CSI consists of 13 items and measures the strain of care provision in five domains (financial, physical, psychological, social and personal)²³. It takes approximately 5 minutes to complete.

Patients and caregivers will also complete a bespoke questionnaire to evaluate the total time associated with attending the hospital or treatment centre for a single ERT administration visit, costs (i.e. out of pocket expenses) and time away from work. In addition, patients will also be asked about their levels of fatigue using a single-item bespoke Likert scale. Bespoke questionnaires will be designed specifically for the purpose of the study.

It is estimated that it will take approximately 25-30 minutes in total for patients to complete their questionnaires (including the second WPAI) and 15-20 minutes for caregivers to complete their questionnaires (including the second WPAI:CG).

Patient questionnaires will be presented in the following order: bespoke Fatigue Likert scale (first completion), SF-12, WHO-5, bespoke patient questionnaire (to be started during the ERT visit and finished at home), bespoke Fatigue Likert scale second and third completion (to be completed on the evening of the ERT administration visit and the next day), WPAI first completion (to be completed at home between 1 and 7 days after the ERT infusion [ideally in first 2 days]), WPAI second completion (to be completed on the day of the patient's next ERT administration visit). Caregiver questionnaires will be presented in the following order: CSI, bespoke caregiver questionnaire (to be started during the ERT administration visit and finished at home), WPAI:CG first completion (to be completed at home between 1 and 7 days after the ERT infusion), WPAI:CG second completion (to be completed on the day of the patient's next ERT administration visit).

The full schedule for completion of the study questionnaires for patients and caregivers is provided in Table 3 below.

Table 3. Timeline of completion and list of questionnaires administered to patients and caregivers

Participant group	Timeline of questionnaire completion			
	During ERT infusion visit	Evening of ERT infusion	1-7 days after ERT infusion	Day of next ERT infusion (~15 days after previous infusion)

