Patients with FD	
 • Bespoke Fatigue Likert scale • SF-12 • WHO-5 • Bespoke patient questionnaire (to be started during ERT infusion visit and finished at home) 	
 • Bespoke Fatigue Likert scale 	
On Day 1 after ERT infusion:
 
 • Bespoke Fatigue Likert scale 
Any day 1-7 after ERT infusion:
 
 • WPAI 	
 • WPAI
Caregivers of patients with FD	
 • CSI • Bespoke caregiver questionnaire (to be started during ERT infusion visit and finished at home) 	-	
Any day 1-7 after ERT infusion:
 
 • WPAI:CG 	
 • WPAI:CG

SF-12: Short Form-12 questions, WHO-5: World Health Organisation 5 questions, WPAI: Work Productivity and Activity Impairment, CG: Caregiver.

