
Summary measures of patients':
 
 • HRQoL (SF-12 scores / responses). • General wellbeing (WHO-5 scores / responses). • Level of fatigue (bespoke Fatigue Likert scale). • Levels of work impairment (WPAI scores / responses). 
Questionnaire scores and/or item responses will be reported using summary statistics, as appropriate to the questionnaire and in accordance with the licensed scoring manual / instructions for use.
	
 • Patient SF-12, WHO-5, Fatigue Likert scale and WPAI responses and dates of completion. For the bespoke Fatigue Likert scale, times (hours and minutes) of completion will also be recorded.

Secondary objective 4: To describe work productivity (measured by the WPAI:CG) and the strain of care provision (measured by the CSI) in caregivers of patients with FD treated with ERT.
	

Summary measures of caregivers':
 
 • Levels of work impairment (WPAI:CG scores / responses). • Levels of strain of providing care for a patient with FD (CSI scores / responses). 	
 • Caregiver WPAI:CG and CSI responses and date of completion.

Questionnaire scores and/or item responses will be reported using summary statistics, as appropriate to the questionnaire and in accordance with the licensed scoring manual / instructions for use.
	

Patients' demographic and clinical characteristics (all patients)
	

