
Summary measures of patients':
 
 ○ HRQoL (SF-12 scores/ responses) ○ General wellbeing (WHO-5 scores / responses). ○ Level of fatigue (bespoke Fatigue Likert scale). ○ Levels of work impairment (WPAI scores / responses) ○ For the bespoke Fatigue Likert scale, times (hours and minutes) of completion will also be recorded. 	
Questionnaire scores and/or item responses will be reported using summary statistics, as appropriate to the questionnaire and in accordance with the licensed scoring manual / instructions for use.
 
For these scores, the total of all items in each of these will be summarized as per section 2.5 for quantitative variables. The frequency and percentages of responses for individual items will also be given. HRQoL and Who-5 will be given for baseline (the data collected during ERT infusion visit). Fatigue score will be given for baseline and the change scores from baseline to score collected at the same day evening of ERT infusion and 15 days after 1st infusion. WPAI scores will be given one at 1-7 days after infusion and change from this to 15 days after infusion.
 
The summary statistics of completion time in minutes will be calculated as per section 2.5 for quantitative variables.

---	---

Secondary objective 4

To describe work productivity (measured by the WPAI:CG) and the strain of care provision (measured by the CSI) in caregivers of patients with FD treated with ERT.

Summary measures of caregivers':
	
Questionnaire scores and/or item responses will be reported using summary statistics, as appropriate to the questionnaire and in accordance with the licensed scoring manual / instructions for use.

---	---

 ○ Levels of work impairment (WPAI:CG scores / responses). ○ Levels of strain of providing care for a patient with FD (CSI scores / responses). 	
The total scores will be summarized as per section 2.5 for quantitative variables. The individual item responses will be presented using frequency and percentages.
 
WPAI-CG will be summarized at 1-7 days after 1st infusion and change from this to 15 days after infusion.
 
CSI scores collected during ERT infusion will be summarized.

Patients' demographic and clinical characteristics (all patients)	

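### Fatigue is rated only around one infusion and at no set hour, so the SAP's visit-to-evening change mixes time of day with infusion effects; its 15-day change has no data and the Day 1 rating has no analysis

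*Protocol*

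**What the plan says.** The fatigue measure is a bespoke single item (Protocol 9.1.2). The protocol is consistent about when it is given.

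- Section 4, Study design: "The Fatigue Likert scale will be completed three times; during an ERT administration visit, on the evening of the visit and the next day".
- 9.1.2 repeats this order, and Table 3 places the third rating "On Day 1 after ERT infusion".
- In the last column of Table 3 (the next infusion, about 15 days on), the only patient form listed is the WPAI.

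No clock hour or window is given for any of the three ratings. Table 4 (9.6) says of this scale that "times (hours and minutes) of completion will also be recorded".

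SAP 2.6, secondary objective 3, calls the visit rating baseline: "Fatigue score will be given for baseline and the change scores from baseline to score collected at the same day evening of ERT infusion". The sentence then adds a second change score, to "15 days after 1st infusion". It does not mention the next-day rating. Completion times are to be summarised, but they play no part in the change scores.

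The WPAI is treated differently. Its second completion exists "to capture a seven day period that does not include ERT administration" (Protocol Section 4).

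**The concern.** The study sets out to quantify the burden of ERT, and its results may go into HTA submissions (Protocol Section 4). In that setting, a score labelled as change from baseline to the evening of an infusion invites the reading that it is fatigue from the infusion. The evening rating will normally also be later in the day than the visit rating, so part of the change may reflect only the hour. For work productivity the protocol built in a period without ERT. For fatigue, the other repeated patient measure, it did not.

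The limitations in 9.11 mention extra tiredness on visit days, but apply it to HRQoL and wellbeing. Time of day is not raised, and 9.9.4 plans no sensitivity analyses.

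There is a second, simpler problem. The SAP and the protocol disagree about which fatigue ratings exist, so part of the planned fatigue analysis cannot be run and part of the data has no planned use.

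**Working it through.** The plan states no sample size, effect size or SD for fatigue, so there is no figure to reproduce. The check has two parts.

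**1. Schedule against analysis**

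| Rating | Protocol (Section 4, 9.1.2, Table 3) | SAP 2.6 |
|---|---|---|
| During the visit | Collected, no hour set | Reported as baseline |
| Same evening | Collected, no hour set | Change from baseline |
| Day 1 after infusion | Collected, no hour set | Not mentioned |
| About day 15 | Not collected (WPAI only) | Change from baseline |

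Two fatigue change scores are planned, and one of them has no data. With about 120 patients expected (Protocol 9.8), the schedule yields 3 × 120 = 360 ratings. Of these, 1 × 120 = 120, one third, have no stated analysis.

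**2. What the visit-to-evening change measures**

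Let u(h) be a patient's usual fatigue at hour h on a day away from infusion. Let A be whatever attendance, pre-medication and any infusion already under way add at the time of the visit rating. Let B be what they add in the evening.

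- Visit rating, at hour v: u(v) + A
- Evening rating, at hour n: u(n) + B
- Change: [u(n) − u(v)] + (B − A) = D + E, where D is ordinary within-day change and E = B − A

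Each patient supplies one such sum. No scheduled rating gives D. More patients narrow the interval around D + E but do not separate the terms.

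*Illustration with assumed values* (the documents give no scale range). A mean change of 1.0 point fits E = 1.0 if D = 0, E = 0.5 if D = 0.5, and E = 0 if D = 1.0.

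*Direction.* As a measure of the evening burden B, the change is off by (D + B − A) − B = D − A. Taking D = 0.5 for illustration:

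- A = 0 gives +0.5 (overstated)
- A = 0.5 gives 0
- A = 1.0 gives −0.5 (understated)

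The documents fix neither D nor A, so the sign is open.

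**What the remedies would identify**

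Let C be the carry-over on Day 1. If the Day 1 rating is taken at hour v, the change from the visit is [u(v) + C] − [u(v) + A] = C − A. The within-day term drops out, provided usual fatigue at that hour is alike on both days. The contrast still starts from a visit-day state, so it is not a pure ERT effect either.

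Ratings at hours v and n on a day away from infusion give D directly, so (visit-day change) − (infusion-free-day change) = B − A. Differences at the same hour give A and B themselves. Both results assume a similar usual profile on the two days.

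**The case against.** The strongest reply is that nothing in the plan attributes fatigue to the infusion. The objective is to describe fatigue levels (Protocol 8.4), the research question concerns the impact of Fabry disease (8.1), there is no hypothesis (8.2), and 9.11 says that confounding will not be controlled. This stands. The point limits what the change score can mean; it does not expose an error in a stated test.

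A reader might go further and infer that the change must overstate ERT fatigue, because people tire towards evening. The documents do not support that. They state no visit hour and report no evening rise. The first rating is placed within the visit, at the head of the forms (9.1.2). The validated forms that follow it are expected to be filled in during the infusion (9.7). Section 7 says pre-medication, including antihistamines, is frequent, and 9.11 says patients may be more tired when attending. Each of these could raise the first rating and shrink the change. For the same reason, no percentage of the change can be assigned to time of day: any such figure would only restate the values assumed.

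A reader might also infer that no day without an infusion is rated. Day 1 is such a day. What is missing is a rating clear of possible carry-over from the infusion.

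Two further replies stand in part. Annex 2 is only a heading in the public text, so the form itself may specify an hour or a recall period. Recorded completion times would allow description by clock time, but the SAP plans only to summarise them.

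Finally, one sentence of limitation would largely deal with the risk of misreading. It would not resolve the 15-day mismatch or give the Day 1 rating an analysis.

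**Conclusion.** The point holds as a limit on interpretation together with a plain mismatch between documents. The visit-to-evening change cannot be read as infusion-related fatigue, and the net direction and size of the distortion are unknown. Of the two fatigue changes in the SAP, one mixes two sources and the other has no data behind it, while the Day 1 rating that is collected has no analysis.

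The effect is confined to one item within a descriptive secondary objective; the primary endpoint, HCP time, is untouched. The conclusion assumes that the visit normally precedes the evening by some hours, which is inferred from the existence of a separate evening rating, and that the questionnaire form does not fix the hours. It does not depend on fatigue rising through the day: if D were negative, the two components would still be inseparable.

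**What to change.** 1. **Protocol 9.1.2 and Table 3:** ask for the Day 1 rating at about the same clock hour as the visit rating. **SAP 2.6:** replace the uncollected 15-day change with this time-matched Day 1 change, and report the evening rating as a level. State there, and in Protocol 9.11, that the visit-to-evening change is not attributable to ERT. Adding a fatigue rating at 15 days would not be a substitute: it would fall on the next infusion day and have no matched evening value away from infusion.

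2. **Preferably also:** add the same one-item rating at the visit hour and in the evening on the day before the next infusion, returned with the second WPAI. Report the visit-day and infusion-free-day changes side by side within patient.

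**Cost.** The first change adds no ratings. The hour is asked of patients at home, and patient-reported data are not queried (9.10), so some will miss it; the recorded times will show how many. The second takes each patient from three to five one-item ratings (2 × 120 = 240 more in all). It needs no extra visit, but adds slight burden, and some ratings will not come back. Both alter the protocol schedule, so ethics committees must be informed (10.2). The SAP edits are cheap, since its table shells are still to be written (SAP 4).

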8.1 Research questions

What is the total HCP time associated with the preparation and administration of a single dose of ERT in patients with FD and the patient and caregiver time and costs (out-of-pocket expenses) associated with an ERT attendance? What is the impact of FD on patients' HRQoL, wellbeing, levels of fatigue and work productivity? What is the burden of care provision for the caregivers of patients with FD and the impact on their work productivity?

8.2 Hypothesis

This is a descriptive study and there is no *a priori* hypothesis to be tested.

8.3 Primary objective

To quantify the total time spent by HCPs in the preparation and administration of a single dose of ERT (with agalsidase alfa and agalsidase beta) in patients with FD.

8.4 Secondary objectives

- To quantify the total patient time, costs (i.e. out of pocket expenses) and work-related absence associated with attendances for the administration of a single dose of ERT (with agalsidase alfa and agalsidase beta) in patients with FD.

- To quantify the total caregiver time, costs (i.e. out of pocket expenses) and work-related absence associated with accompanying a patient with FD for the administration of a single dose of ERT (with agalsidase alfa or agalsidase beta).
- To describe patient-reported HRQoL (measured by the 12 Item Short Form Survey [SF-12]), wellbeing (measured by the World Health Organization-5 Wellbeing Index [WHO-5]), levels of fatigue (measured by a bespoke Fatigue Likert scale) and work productivity (measured by the Work Productivity and Activity Index [WPAI] questionnaire) in patients with FD treated with ERT.
- To describe work productivity (measured by the WPAI-CG) and the strain of care provision (measured by the Caregiver Strain Index [CSI]) in caregivers of patients with FD treated with ERT.

9. Research methods

This study has been designed and will be conducted according to the requirements of the European Network of Centres for Pharmacoepidemiology and Pharmacovigilance (ENCePP; <http://www.encepp.eu/index.shtml>) and International Society for Pharmacoepidemiology (ISPE; https://www.pharmacoepi.org/resources/guidelines_08027.cfm) guidance, as appropriate.

9.1 Study design

This is an international, non-interventional research study of adult patients with FD and their caregivers. The study will comprise a prospective time and motion evaluation and a cross-sectional evaluation of patient- and caregiver-reported outcomes (including HRQoL, wellbeing, levels of fatigue and work-productivity [for patients with FD]; work productivity and the strain of care provision [for caregivers]). Patients' demographic characteristics will be collected from hospital medical records. No changes to routine patient management will be made for the purposes of any part of this study and there is no requirement for additional visits or investigations.

Separate patient consent will be obtained for the time and motion evaluation and the cross-sectional evaluation of patient-reported HRQoL, wellbeing, levels of fatigue and work productivity; thus, patients who do not wish to complete the study questionnaires will remain

eligible for the time and motion study (and vice versa), provided that consent has been obtained. Caregivers will consent to completion of the study questionnaires.

A prospective design for collection of patient-centred outcomes data was selected since it is unlikely that these will be documented in medical records. A prospective design is the only appropriate method for collecting time and motion and caregiver-reported outcomes data.

Based on the rarity of FD, the broad eligibility criteria and the number and types of participating centres, the results of this study should be generalisable to the wider patient population with FD treated with ERT with agalsidase alfa or agalsidase beta in routine clinical practice in the participating countries.

9.1.1 Prospective time and motion study

Patients with FD attending the hospital or treatment centre for administration of a single dose of ERT (with agalsidase alfa or agalsidase beta) during the prospective recruitment period will be observed by an independent researcher or a member of their care team for the duration of their episode of care. The observer will record the HCP time associated with all activities relating to the preparation and administration of ERT (including the pre-infusion clinical assessment and post-administration documentation). It is possible that a single patient may present to the hospital or treatment centre for administration of ERT multiple times within the recruitment period (when they return for follow-up treatment), but repeated observation of the same patient will ideally be capped at two episodes of care per patient, to minimise bias from multiple observations of patients with atypical resource use. For countries with limited FD patient numbers, a review of episodes of care observed will be completed on an ongoing basis. It may be determined that it is possible to observe three episodes per patient in these circumstances, however only two episodes will be observed per patient wherever possible. For patients who are eligible to be observed more than once, initial consent for observation of up to three episodes of care will be obtained, and will be confirmed verbally by their HCP before the second or third episode of care is observed.

9.1.2 Cross sectional evaluation of patient- and caregiver-reported outcome measures

Patients with FD and their caregivers will be asked to complete a series of questionnaires, to include validated measures of HRQoL, wellbeing and work productivity (for patients); and work productivity and the strain of care provision (for caregivers).

Questionnaires were selected based on their ease of use, short time required for completion (in order to minimise the burden on patients), availability in the required languages, and the fact that they have been previously validated in a similar context to our study:

- HRQoL will be assessed using the SF-12 version 2. The SF-12 is a shorter version of the 36 item Short Form Survey (SF-36) that uses 12 questions to measure functional health and wellbeing from the patients' point of view. It is made up of 8 domains: physical functioning, bodily pain, general health, vitality, physical role, role emotional, social functioning and mental health¹⁹. These 8 domains form 2 subscales: physical component summary and mental component summary. The SF-12 was chosen for the present study as it was used in a recent registry of patients with FD²⁰ and is less burdensome for patients to complete than the longer SF-36. It has a short completion time (approximately 5 minutes) and is available in all 4 languages of the study countries.
- Patients' general wellbeing will be assessed using the WHO-5²². It consists of 5 items and the timeframe for responses is based on the previous 2 weeks. The 5 items relate to feeling cheerful, calm, active, rested and being interested in life. The WHO-5 was selected to assess the impact of FD and its treatment on patients' well-being. It is quick and easy to complete (<5 minutes) and score.
- The impact of FD on patients' work lives will be assessed using the WPAI. The WPAI consists of 6 items. The WPAI was chosen for the present study as it is quick to complete (<5 minutes) and is available in all 4 languages of the countries selected in this study.

Caregiver-reported outcomes will be evaluated using the following validated questionnaires addressing work productivity and the strain of care provision:

- The impact of caring for a patient with FD on caregivers' work lives will be assessed using the WPAI specific to caregivers (WPAI:CG)²⁴. The WPAI:CG consists of 6 items and was chosen for the present study as it is quick to complete (<5 minutes) and is available in all 4 languages of the study countries.

- The strain of providing care for a patient with FD will be assessed using the CSI. The CSI consists of 13 items and measures the strain of care provision in five domains (financial, physical, psychological, social and personal)²³. It takes approximately 5 minutes to complete.

Patients and caregivers will also complete a bespoke questionnaire to evaluate the total time associated with attending the hospital or treatment centre for a single ERT administration visit, costs (i.e. out of pocket expenses) and time away from work. In addition, patients will also be asked about their levels of fatigue using a single-item bespoke Likert scale. Bespoke questionnaires will be designed specifically for the purpose of the study.

It is estimated that it will take approximately 25-30 minutes in total for patients to complete their questionnaires (including the second WPAI) and 15-20 minutes for caregivers to complete their questionnaires (including the second WPAI:CG).

Patient questionnaires will be presented in the following order: bespoke Fatigue Likert scale (first completion), SF-12, WHO-5, bespoke patient questionnaire (to be started during the ERT visit and finished at home), bespoke Fatigue Likert scale second and third completion (to be completed on the evening of the ERT administration visit and the next day), WPAI first completion (to be completed at home between 1 and 7 days after the ERT infusion [ideally in first 2 days]), WPAI second completion (to be completed on the day of the patient's next ERT administration visit). Caregiver questionnaires will be presented in the following order: CSI, bespoke caregiver questionnaire (to be started during the ERT administration visit and finished at home), WPAI:CG first completion (to be completed at home between 1 and 7 days after the ERT infusion), WPAI:CG second completion (to be completed on the day of the patient's next ERT administration visit).

The full schedule for completion of the study questionnaires for patients and caregivers is provided in Table 3 below.

Table 3. Timeline of completion and list of questionnaires administered to patients and caregivers

Participant group	Timeline of questionnaire completion			
	During ERT infusion visit	Evening of ERT infusion	1-7 days after ERT infusion	Day of next ERT infusion (~15 days after previous infusion)
Patients with FD	
 • Bespoke Fatigue Likert scale • SF-12 • WHO-5 • Bespoke patient questionnaire (to be started during ERT infusion visit and finished at home) 	
 • Bespoke Fatigue Likert scale 	
On Day 1 after ERT infusion:
 
 • Bespoke Fatigue Likert scale 
Any day 1-7 after ERT infusion:
 
 • WPAI 	
 • WPAI
Caregivers of patients with FD	
 • CSI • Bespoke caregiver questionnaire (to be started during ERT infusion visit and finished at home) 	-	
Any day 1-7 after ERT infusion:
 
 • WPAI:CG 	
 • WPAI:CG

SF-12: Short Form-12 questions, WHO-5: World Health Organisation 5 questions, WPAI: Work Productivity and Activity Impairment, CG: Caregiver.

